17.2 Confidentiality Regarding Trial Patients

The Investigator must ensure the privacy of the patients, including their personal identity and all personal medical information, will be maintained at all times. In CRFs and other documents submitted, patients will not be identified by their names, but by an identification code (e.g. patient ID number).

A monitor, properly authorised persons on behalf of the Sponsor's quality assurance unit or competent authorities may scrutinise personal medical information for the purpose of verifying data recorded on the CRF. Personal medical information will always be treated as confidential, according to local privacy regulations.

17.3 Trial Management Committee (TMC)

The TMC will initially meet to assess safety after 3 patients in each arm has completed 8 cycles of pembrolizumab. Thereafter, the TMC will meet at 6 monthly intervals.

The TMC will comprise the following members:

- Radiation Oncology Principal Investigator
- Medical Oncology Principal Investigator
- An Independent Research Physician
- Clinical Trial Manager
- Trial Statistician

The C/PI will receive and review SAEs in real time.

The TMC will receive periodic safety reports therefore facilitating a response to potential safety issues. The TMC will also oversee study planning, monitoring, progress, review of information from related research, and implementation of recommendations from other study committees and external bodies (e.g. ethics committees). The primary mandate of the TMC would be to protect patient safety. If adverse events of a particularly serious type are more common than anticipated, the study can be considered for termination. Please see SABRseq TMC terms of reference for further information.

The TMC will consider whether to continue the study as planned, modify, or stop it, based on reports provided by BaCT or other information.

18. Publication and Presentation Policy

18.1 Reporting of Results

The Trial Management Committee will be responsible for decisions regarding presentations and publications arising from this trial according to the Sponsor Authorship, Publication and Spokesmanship Guidelines.

The statistician will perform the primary analysis of trial results, for publication. The principal investigator will publish the primary trial results.

Publications and abstracts must be presented to the TMC Sponsor (OCR) for review and approved prior to submission.


Appendix 1

ECOG Performance Status Criteria

Grade ECOG

- 0 Fully active, able to carry on all pre-disease performance without restriction.
- 1 Restricted in physically strenuous activity but ambulatory and able to carry out work of a light or sedentary nature, e.g., light house work, office work.
- 2 Ambulatory and capable of all self care but unable to carry out any work activities. Up and about more than 50% of waking hours.
- 3 Capable of only limited self care, confined to bed or chair more than 50% of waking hours.
- 4 Completely disabled. Cannot carry on any self care. Totally confined to bed or chair.
- 5 Dead

As published in Am. J. Clin. Oncol.:

Appendix 2

Spine Instability Neoplastic Score (SINS)

SINS Component	Score
Location	
Junctional (occiput-C2, C7-T2, T11-L1, L5-S1)	3
Mobile spine (C3-C6, L2-L4)	2
Semirigid (T3-T10)	1
Rigid (S2-S5)	0
Pain*	
Yes	3
Occasional pain but not mechanical	1
Pain-free lesion	0
Bone lesion	
Lytic	2
Mixed (lytic/blastic)	1
Blastic	0
Radiographic spinal alignment	
Subluxation/translation present	4
De novo deformity (kyphosis/scoliosis)	2
Normal alignment	0
Vertebral body collapse	
> 50% collapse	3
< 50% collapse	2
No collapse with > 50% body involved	1
None of the above	0
Posterolateral involvement of spinal elements†	
Bilateral	3
Unilateral	1
None of the above	0

Appendix 3

RECIST 1.1 criteria- Response Evaluation Criteria in Solid Tumours

These instructions are based on the guidelines recommended in Eisenhower et al., 2009 .

3. Disease and lesion definitions

3.1 Measurable Disease

Measurable tumour lesions are defined as those that can be accurately measured in at least one dimension (longest diameter to be recorded) as

- ≥ 10 mm with CT scan or clinical examination.
- Bone lesions are considered measurable only if assessed by CT scan and have an identifiable soft tissue component that meets these requirements (soft tissue component ≥ 10 mm by CT scan).
- Malignant lymph nodes must be ≥ 15 mm in the short axis to be considered measurable; only the short axis will be measured and followed.

All tumour measurements must be recorded in millimetres. Previously irradiated lesions are not considered measurable unless progression has been documented in the lesion.

3.2 Non-measurable Disease

All other lesions, including small lesions (longest diameter < 10 mm or pathological lymph nodes with ≥ 10 to < 15 mm short axis) as well as truly non-measurable lesions. Lesions considered truly non-measurable include: leptomeningeal disease, ascites, pleural or pericardial effusion, inflammatory breast disease, lymphangitis cutis/pulmonis, abdominal masses/abdominal organomegaly identified by physical exam that is not measurable by reproducible imaging techniques.

All measurements should be taken and recorded in metric notation, using callipers if clinically assessed. All baseline evaluations should be performed as closely as possible to the beginning of treatment and never more than 4 weeks before the beginning of the treatment.

The same method of assessment and the same technique should be used to characterize each identified and reported lesion at baseline and during follow-up.

Clinical lesions will only be considered measurable when they are superficial (e.g., skin nodules and palpable lymph nodes). For the case of skin lesions, documentation by colour photography, including a ruler to estimate the size of the lesion, is recommended.

3.3 Methods of Measurement

- CT and MRI are the best currently available and reproducible methods to measure target lesions selected for response assessment. Conventional CT and MRI should be performed with cuts of 10 mm or less in slice thickness contiguously. Spiral CT should be performed using a 5 mm contiguous reconstruction algorithm. This applies to tumours of the chest, abdomen and pelvis. Head and neck tumours and those of extremities usually require specific protocols.
- Lesions on chest X-ray are acceptable as measurable lesions when they are clearly defined and surrounded by aerated lung. However, CT is preferable.

3.4 Baseline documentation of “Target” and “Non-Target” lesions

- All measurable lesions up to a maximum of two lesions per organ and 5 lesions in total, representative of all involved organs should be identified as **target lesions** and recorded and measured at baseline.
- Target lesions should be selected on the basis of their size (lesions with the longest diameter), be representative of all involved organs and should be those that lend themselves to reproducible repeated measurements. On occasion, the largest lesion may not lend itself to reproducible measurement, in which circumstance the next largest lesion, which can be measured reproducibly, should be selected.
- Only the short axis of lymph nodes identified as target lesions contribute to the baseline sum. The short axis of the node is the diameter normally used by radiologists to judge if a node is involved by solid tumour.
- A sum of the diameters (longest for non-nodal lesions, short axis for nodal lesions) for all target lesions will be calculated and reported as the baseline sum diameters. The baseline sum diameters will be used as reference by which to characterise the objective tumour.
- All other lesions (or sites of disease) including pathological lymph nodes should be identified as **non-target lesions** and should also be recorded at baseline. Measurements of these lesions are not required, but the presence, absence, or in rare cases ‘unequivocal progression’ of each should be noted throughout follow-up. In addition, it is possible to record multiple non-target lesions involving the same organ as a single item on the case report form (e.g. multiple enlarged pelvic lymph nodes or multiple liver metastases’.

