5.3 Endpoints

Primary Endpoint

- Toxicities associated with SABR in combination to pembrolizumab are defined as adverse events (AE's) considered possibly, probably or definitely related to the treatment. Safety (acute and long term) will be assessed using CTCAE version 4.03.

Secondary Endpoints:

- Response will be assessed by 4 different methods (RECIST 1.1, irRECIST, Peter Mac Metabolic Response Criteria and PERCIST 1.0) and will be assessed a) only considering irradiated lesions; b) only considering non-irradiated lesions and; c) considering all lesions (overall response rate)
- Overall survival will be measured from the date of randomisation to the date of death from any cause.
- Progression free survival will be measured from the date of randomisation to the date of first progression at any site or date of death due to any cause.
- Event history is defined as the time from the date of randomisation to the date of each event of interest (progression at an irradiated lesion, progression at a non-irradiated lesion, appearance of a new lesion, ceasing treatment and death). Patients alive will be censored at the date of last follow-up.

Exploratory Endpoints

A number of translational endpoints will be evaluated including:

- PD-L1 expression in tumour tissue using immunohistochemistry with the 22C3 antibody using the DAKO Autolink 48 system.

- Tumour infiltrating lymphocytes (TILs).
- Changes in host anti-tumour immunity to look for evidence of immune activation and relief of immunosuppression in tumour tissue and peripheral blood from the patient over time and at time of progression (if this occurs).
 - Blood samples will be collected at multiple time points before, during and after trial related therapies. These will be analysed for biomarkers including, but not limited to, the following (this is a non-exhaustive list):
 - Absolute lymphocyte counts using a blood analyser.
 - The presence of CD8+ T cells by flow cytometric analysis.
 - Change in frequency of tumour reactive T cells. These may include markers for HLA-DR, CD4+, CD8+ T cells, PD-1, TIM-3 signifying antigen presentation and experience.
 - Immune cytokines

6. Trial Design

This is a prospective, open label, two arm randomised clinical trial with 1:1 allocation ratio evaluating the safety, efficacy and immunological effects of two different sequences of pembrolizumab in combination with SABR treatment in NSCLC – pembrolizumab given either before or after SABR.

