7.1 Inclusion Criteria

In order to be eligible for participation in this trial, the patient must:

1. Have provided written informed consent for the trial.
2. Be ≥ 18 years of age on day of signing informed consent.
3. Have at least one lesion not planned for SABR that is measurable disease based on RECIST 1.1.
4. Patients must have a histologically or cytologically confirmed metastatic non-small cell lung cancer.
5. Patients with disease previously untreated with systemic therapy must have $\geq 1\%$ PD-L1 staining and patients who have previously received systemic therapy must have $\geq 1\%$ PD-L1 staining on immunohistochemistry
6. Patients must have at least 1-3 lesions suitable for treatment with stereotactic radiotherapy.
7. Be willing to provide tissue from a newly obtained core or excisional biopsy of a tumour lesion where feasible. *Newly-obtained is defined as a specimen obtained up to 12 weeks prior to randomisation. Patients for whom newly-obtained samples cannot be provided (e.g. inaccessible or patient safety concern) may submit an archived specimen only upon agreement from the study principal investigators.*
8. Have a performance status of 0-1 on the ECOG Performance Scale (see Appendix 1).

9. Demonstrate adequate organ function as defined in table 3 below, all screening labs should be performed within 10 days of randomisation.

Table 3 Adequate Organ Function Laboratory Values

System	Laboratory Value
Haematological	
Absolute neutrophil count (ANC)	$\geq 1.5 \times 10^9 / \text{L}$
Platelets	$\geq 100 \times 10^9 / \text{L}$
Haemoglobin	$\geq 90 \text{ g/L}$ without transfusion or EPO dependency (within 7 days of assessment)
Renal	
Serum creatinine OR Measured or calculated ^a creatinine clearance (GFR can also be used in place of creatinine or CrCl)	$\leq 1.5 \times$ upper limit of normal (ULN) OR $\geq 30 \text{ mL/min}$ for patients with creatinine levels $> 1.5 \times$ institutional ULN
Hepatic	
Serum total bilirubin	$\leq 1.5 \times$ ULN OR Direct bilirubin \leq ULN for patients with total bilirubin levels $> 1.5 \text{ ULN}$
AST (SGOT) and ALT (SGPT)	$\leq 2.5 \times$ ULN OR $\leq 5 \times$ ULN for patients with liver metastases
Coagulation	
International Normalized Ratio (INR) or Prothrombin Time (PT)	$\leq 1.5 \times$ ULN unless patient is receiving anticoagulant therapy as long as PT or PTT is within therapeutic range of intended use of anticoagulants

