9.3 Treatment Schedule

Study therapy should commence within 28 days of patient randomisation on the study. A single dose of 20 Gy should be prescribed, although a single 18Gy fraction can be used as an alternative for a centrally located lung lesion or a spinal lesion with a SINS score of ≥ 7 after review at SABR chart round. Ideally all treatments should be performed on the same day. One or more lesions must be deemed suitable for treatment with SABR; up to 3 lesions may be treated. The choice of treatment sites for SABR is at clinician discretion, but should encompass different types of metastatic sites where possible (e.g. bone and/or lymph node and/or visceral organ). The maximal number of metastases within this range should be irradiated, however, at least one metastases defined as measurable disease must not be irradiated. The use of single 4mg dose of prophylactic dexamethasone prior to SABR treatment is permitted.

10. Trial Pembrolizumab Treatment

Pembrolizumab treatment should begin either 7 days (+/- 2 days) before the first SABR treatment or 7 days (+/- 2 days) after the last SABR treatment

Pembrolizumab 200 mg will be administered as a 30 minute IV infusion every 3 weeks for 34 cycles. Sites should make every effort to target infusion timing to be as close to 30 minutes as possible. However, given the variability of infusion pumps from site to site, a window of -5 minutes and +10 minutes is permitted (i.e., infusion time is 30 minutes: -5 min/+10 min).

Pembrolizumab treatment should be administered on Day 1 of each cycle after all procedures/assessments have been completed as detailed in Sections 8.2 and 8.3. Trial treatment may be administered up to 3 days before or after the scheduled Day 1 of each cycle due to administrative reasons.

All trial treatments will be administered on an outpatient basis.

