13.3 PERCIST 1.0 Criteria

A region of interest (ROI) is used to assess the maximum SUL peak. This ROI is typically the region of the baseline tumour with the highest uptake, but it can also be another lesion that was previously present and is the most active lesion after treatment.

- **Complete metabolic response (CMR):** complete resolution of ^{18}F -FDG uptake within the measurable target lesion so that it is less than mean liver activity and indistinguishable from surrounding background blood-pool levels. Disappearance of all other lesions to background blood-pool level.
- **Partial metabolic response (PMR):** reduction greater or equal to 30% in the target measurable tumour ^{18}F -FDG SUL peak.
- **Stable metabolic disease (SMD):** disease other than CMR, PMR or PMD.
- **Progressive metabolic disease (PMD):** Greater than 30% increase in ^{18}F -FDG SUL peak OR visible increase in extent of ^{18}F -FDG tumour uptake (75% of total lesion glycolysis volume with no decline in SUL OR the advent of new ^{18}F -FDG-avid lesions that are typical of cancer and not related to treatment effect or infection.

14. Statistical Considerations

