14.7 Response Analysis

All tumour response measurements (pre- and post-treatment) must be recorded using the definitions of RECIST 1.1. RECIST assessments will take into account post-treatment inflammatory processes that occur after SABR treatment in pulmonary and liver tissues. PET response criteria will also be assessed and reported. If a criterion is met in more than one response type then the response type will be classified at the lowest possible level. The initial assessment of response will be determined after all protocol treatment has been completed, whether or not all of the planned treatment was received. In addition, irRECIST, PERCIST and Peter Mac Metabolic Response criteria will be considered in conjunction to RECIST 1.1. Metabolic response criteria and PERCIST 1.0 results or assessments will not be entered by site clinical staff and will be reported centrally. Overall patient's response rates

(CR+PR at all lesions) at 6 and 12 months after commencement of SABR treatment will be described as percentages with exact 95% confidence interval. Overall response for all irradiated lesions and un-irradiated lesions will also be assessed separately. Lesion size of measurable lesions may be plotted over time to describe patient response trajectories. Overall response rates will be compared between treatment arms using Fisher's exact test.

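### RECIST target lesions are chosen as one pooled set without regard to SABR status, so response in the irradiated or the non-irradiated lesions can be left without a measured basis

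*Combined protocol and SAP*

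**What the plan says.** Response is a secondary endpoint. Under section 5.3 it is assessed "a) only considering irradiated lesions; b) only considering non-irradiated lesions and; c) considering all lesions (overall response rate"), by four criteria. Section 5.2 compares these results between arms. Section 14.7 repeats the requirement: "Overall response for all irradiated lesions and un-irradiated lesions will also be assessed separately".

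The measurement rule is in Appendix 3, section 3.4. Targets are "All measurable lesions up to a maximum of two lesions per organ and 5 lesions in total, representative of all involved organs". They are ranked by size, with organ representation and reproducibility also considered. Every other lesion is non-target, and "Measurements of these lesions are not required". SABR status is not mentioned. Appendix 3, section 3.5, defines partial response as a fall of at least 30% in the sum of target diameters. Appendix 4 takes its measurability and baseline lesion definitions from RECIST 1.1 and says in section 2.2 that non-target lesions do not affect irPR.

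Inclusion criterion 3 requires the patient to "Have at least one lesion not planned for SABR that is measurable disease based on RECIST 1.1". No criterion requires a SABR lesion to be measurable. Sections 9 and 9.3 call for as many lesions as possible, up to three, to be irradiated while sparing a measurable one. Section 9.3 leaves site choice to the clinician and says that it "should encompass different types of metastatic sites where possible (e.g. bone and/or lymph node and/or visceral organ").

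**The concern.** The endpoint needs two lesion sets, each with its own baseline sum of diameters, and the method supplies one pooled set. Criterion 3 ensures that a measurable spared lesion exists, but nothing makes it a target. If it is not a target, it need not be measured, and shrinkage of 30% or more in it has no route to a RECIST partial response.

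Response in spared lesions is where a difference between sequences in systemic shrinkage would appear. Whether a patient can contribute would then depend on where the lesions lie and which were irradiated, not on treatment effect. With 16 patients per arm, one patient is 1/16 = 6.25 percentage points.

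**Working it through.** **1. The plan's own figures.** Table 10 (section 14.9) gives intervals for n = 16. The exact 95% limits are the 2.5% quantile of Beta(x, n−x+1) and the 97.5% quantile of Beta(x+1, n−x). For x = 6, 8, 10 and 12 they are 15.2–64.6, 24.7–75.3, 35.4–84.8 and 47.6–92.7. Table 10 is reproduced.

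**2. A permitted patient.** Take measurable disease in the lung only, with lesions of 40, 35 and 20 mm.
- Up to three lesions may be irradiated and one measurable lesion must be spared, so at most two are irradiated. Suppose these are the 40 and 35 mm lesions.
- The targets are the two largest in the organ, which are the same two lesions.
- The 20 mm lesion satisfies criterion 3 but is non-target. If it shrinks to 14 mm (20 × 0.7, a 30% fall), no diameter has to be recorded and the non-irradiated set has no sum.
- Table 3.7 in Appendix 3 has no row that scores response in a set without targets.

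**3. Can both sets be left without a target?** Assume that all m measurable lesions are in one organ, the targets are the two largest, and k lesions are irradiated at random with respect to size.
- No target in the non-irradiated set: k(k−1)/[m(m−1)]. For m/k = 3/2, 4/3, 5/3 and 6/3 this is 2/6 = 33%, 6/12 = 50%, 6/20 = 30% and 6/30 = 20%.
- No target in the irradiated set: (m−k)(m−k−1)/[m(m−1)]. For 5/3 and 6/3 this is 2/20 = 10% and 6/30 = 20%. If only one lesion is suitable for SABR, 3/1 and 4/1 give 2/6 = 33% and 6/12 = 50%.

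These figures show that both cases can occur. They are not expected frequencies, because the documents give no lesion distribution.

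**4. A second, separate cause.** Appendix 3, section 3.1, counts bone lesions as measurable only with a soft tissue component. A patient whose only SABR sites are bone lesions without one has no measurable irradiated lesion under any selection rule.

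**5. Effect on a class-specific rate.** Assume 16 patients, 50% true response, j patients without a target in the class, half of them true responders, and all of those by partial response. Counting the j patients as non-responders lowers the rate by j × 0.5/16, or 3.125 points per affected patient. Excluding them keeps the rate at 50% with fewer patients.

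| j (assumed) | Counted as non-responders | Excluded |
|---|---|---|
| 0 | 8/16 = 50% (24.7–75.3) | 8/16 = 50% (24.7–75.3) |
| 2 | 7/16 = 43.75% (19.8–70.1) | 7/14 = 50% (23.0–77.0) |
| 4 | 6/16 = 37.5% (15.2–64.6) | 6/12 = 50% (21.1–78.9) |
| 6 | 5/16 = 31.25% (11.0–58.7) | 5/10 = 50% (18.7–81.3) |
| 8 | 4/16 = 25% (7.3–52.4) | 4/8 = 50% (15.7–84.3) |

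The plan does not say which column applies. Section 14.3 makes a treated patient response-evaluable on having a CT or PET scan, which suggests inclusion. Table 3.7 has a not-evaluable category, and section 14.7 does not say how it is counted.

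**6. PET.** PERCIST (section 13.3) uses one region of interest: "This ROI is typically the region of the baseline tumour with the highest uptake". After treatment it may be a different lesion. One region per patient does not give two class-specific results. The Peter Mac criteria (section 13.2) already work lesion by lesion, but their complete-response definition refers to the radiation treatment volume, which a spared lesion does not have. Footnote 11 to the schedule places FDG-PET only at baseline and before cycle 5, so later assessments rest on CT.

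**The case against.** The best counter-argument is that restricting the assessment to one class of lesions, as section 5.3 does, already implies applying Appendix 3 within that class. This reading is plausible. With criterion 3 it would give every patient a non-irradiated target. But no section says so, and a radiologist following Appendix 3 would build one pooled set. Nor would it help where no SABR lesion is measurable. Section 9.3 also spreads SABR across site types where possible, which makes the lung-only example less likely without ruling it out.

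A reader might infer more than the documents support:
- *That partial response becomes impossible.* For RECIST the scoring is undefined: the partial-response row of table 3.5 has a non-target cell, complete response by disappearance remains conceivable, and a metabolic partial response on PET remains available.
- *That the class rates are biased downward.* This follows only if affected patients are counted as non-responders.
- *That the data are lost.* Scans are scheduled throughout, section 16.3 protects images from destruction without written agreement, and section 14.7 allows measurable lesion sizes to be plotted. Diameters could be re-read, although choosing lesions afterwards in an open-label trial is weaker than choosing them at baseline.
- *That non-irradiated response is the only evidence of systemic effect.* Event history (progression in spared lesions, new lesions), PFS and OS also bear on it, although none records shrinkage.
- *That a bone-only SABR patient shows the target rule failing.* That case comes from non-measurable disease, and section 9.3 does not ask for a lone bone lesion.

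**Conclusion.** The concern holds as a gap between endpoint and method. Appendix 3, section 3.4, does not ensure a target lesion in each class, and the plan has no scoring rule for a class without one. Confidence in the textual gap is high.

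The size is unknown because the documents give no distribution of lesions by organ, size or SABR status. At an assumed 4 of 16 affected and 50% true response, the cost is either 12.5 points of downward bias or an interval that widens from 50.6 points (24.7–75.3) to 57.8 points (21.1–78.9). These figures are illustrations, not estimates.

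The endpoint is secondary. The primary toxicity objective and the sample size of 32 are unaffected. The change is still worth making, because the class-specific responses are stated objectives and the remedy uses scans already scheduled.

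**What to change.** In Appendix 3, section 3.4, and section 13:
- Choose target lesions within each class at baseline: all measurable SABR lesions (at most three), and measurable non-SABR lesions up to the usual cap, always including the lesion that met inclusion criterion 3.
- Compute separate sums of diameters for (a) irradiated and (b) non-irradiated lesions. Derive (c) overall response from the standard five-lesion set, and state that (c) may differ from (a) and (b).
- State how new lesions count towards (a) and (b).
- Score a set with no measurable lesion as not evaluable by RECIST and irRECIST, and report the denominator for each set by arm.
- Use one PERCIST region of interest per class, and define the Peter Mac complete response for non-irradiated lesions against adjacent background.

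The cost is revised appendix and CRF wording, slightly more reading time per scan, and a smaller stated denominator for (a). No additional imaging and no change to treatment is needed.
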